4. STUDY DESIGN

Forty dyads will be enrolled in a single-arm mixed methods intervention trial in order to evaluate the feasibility of enrolling older patients with advanced cancer, older patients with advanced cancer and MCI, and their caregivers. This single-arm feasibility study will allow the PI and the team to develop and examine the feasibility of a telehealth-based DLR intervention that has not previously been adapted or tested in these populations. A pre-post test design will be used to measure effects of the DLR intervention on the primary outcome of psychological distress in caregivers. Patients and caregivers will undergo separate semi-structured interviews.

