4.1 SUBJECT POPULATION

4.1.1 Subject Characteristics

a) **Number of Subjects:** We propose to enroll a total of 40 dyads. We will recruit at least 20 dyads of older patients with both advanced cancer and MCI and their caregivers.

All dyads will be recruited via cancer clinics in the University of Rochester/Wilmot Cancer Institute (URWCI) catchment area.

b) **Gender and Age of Subjects:** We intend to recruit across the gender spectrum, including females and males. Patients will be ≥ 65 , with no upper age limit. Caregivers of all older patients will be ≥ 50 , also with no upper age limit. Based on a previous study by our team⁵ we anticipate more female caregivers to enroll, as general caregivers within the population caring for older adults with cancer and/or MCI are predominantly female. Using these previous demographics, we anticipate the following breakdown of caregiver/patient dyads:

Dyad Gender Combinations	Percentage of sample
Male Patient/Male Caregiver	10%
Male Patient/Female Caregiver	40%
Female Patient/Female Caregiver	20%
Female Patient/Male Caregiver	30%

c) **Racial and Ethnic Origin:** There are no exclusion criteria based on racial and ethnic origin. We expect the sample to be representative of the population of older patients with advanced cancer and their caregivers seen at URWCI and living in the WCI catchment area.

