Experience (PEACE)		coping with an illness
Control Preference Scale	Exploratory Aim 1.5.2: communal coping domain	Measurement of perceived control in how people make treatment decisions with life-threatening disease
Inclusion of Other in Self	Exploratory Aim 1.5.2: communal coping domain	Perceived closeness the respondent feels with another person
Interpersonal Needs Questionnaire	Exploratory Aim 1.5.2: communal coping domain	Relationship belonging and perceived burden

Heart Rate Variability (HRV) will be calculated with the ambulatory monitoring heart-rate device Firstbeat Bodyguard 2® that measures RR intervals with a rating sample of 1 ms. The device utilizes a valid and reliable method for sampling RR intervals and provides software to analyze the raw data. We will calculate two time and frequency domain measures of HRV: SDNN (the standard deviation of all normal RR intervals measured between consecutive sinus beats), and RMSSD (the root mean square of successive differences between adjacent normal R-R intervals). In addition, we will measure frequency domain measures, natural log of high frequency (HF, total spectrum power of all NN intervals between 0.15 to 0.4 Hz) for vagal tone/RSA, natural log of low frequency (LF, total spectrum power of all NN intervals between 0.04 to 0.15 Hz), and LF/HF ratio. The use of HRV in this study will be to explore the feasibility of collecting HRV data via telehealth in this method and with this included dyad population. Additionally, there are links between HRV and stress management and emotional regulation.²⁰ This exploratory measure will provide information about HRV, stress management, and emotions in older patients with cancer and their caregivers to improve the intervention and power future studies.

Time Point 1 Measures: Patients and Caregivers will complete the baselines, time point 1 measures within two weeks of beginning their DLR intervention.

Time Point 2 Measures: The same measures provided at baseline, will be repeated within two weeks after the conclusion of the DLR intervention.

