16. DATA ANALYSIS PLAN

16.1 Sample Size Considerations: In order to assess feasibility, using a reference of 0.5 for consent and adherence rate, 40 dyads would achieve 83% power using a one-tailed test at significance of 0.05. The quantitative data will be used to guide sample size calculations for a future randomized pilot. Therefore, a sample of 40 patient/caregiver dyads will support the assessment of feasibility of the telehealth DLR with older patients and caregivers and allow for thematic saturation through qualitative semi-structured interviews.

16.2. Analysis of Aims:

16.2.1 Primary aim: To evaluate the feasibility of enrolling and delivering the telehealth DLR intervention, we will calculate proportion of: 1) approached patient/caregiver dyads who enrolled (70%); 2) enrolled dyads who completed all 8 DLR sessions (70%); and 3) general acceptability of the DLR intervention by patients and caregivers. General acceptability will be examined through coding of transcribed semi-structured interviews from the 40 dyads (separate interviews for patients and caregivers; 40 patient interviews and 40 caregiver interviews). A sub-group analysis will examine any differences between older patients with only advanced cancer and their caregivers and older patients with both advanced cancer and MCI and their caregivers in enrollment, adherence, and acceptability.

16.2.2 Secondary and Exploratory Aims: To examine the pre-post change in caregiver psychological distress, we will utilize a regression analysis that will include the pre-measurement of caregiver distress as a covariate. We will also include gender and income as covariates in this model. A regression analysis will also be used to examine changes in the exploratory measures using the same covariates. A sub-group analysis will compare the difference in changes from pre to post intervention between dyads that include older patients with only advanced cancer and dyads with older patients with both advanced cancer and MCI.

16.2.3 Mixed Methods Aim:

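### Section 16.2.2, read literally, adjusts the exploratory measures for baseline caregiver distress rather than each measure's own baseline; naming the own baseline is a free improvement of low severity

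*Combined protocol and SAP*

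**What the plan says.** Section 16.2.2 (Secondary and Exploratory Aims) first sets out the model for caregiver distress, a "regression analysis that will include the pre-measurement of caregiver distress as a covariate". It adds: "We will also include gender and income as covariates in this model". The next sentence turns to the exploratory measures: "A regression analysis will also be used to examine changes in the exploratory measures using the same covariates". No sentence names an exploratory measure's own baseline value as a covariate.

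The tables in section 8.1 assign four scales to exploratory aim 1.5.2, and both patients and caregivers complete them: PEACE, Control Preference, Inclusion of Other in Self, and Interpersonal Needs. HRV is also exploratory and is recorded from both members of the dyad. Baseline values are part of the schedule. Of Time Point 2, section 8.1 says: "The same measures provided at baseline, will be repeated within two weeks after the conclusion of the DLR intervention".

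The study has one arm: "Forty dyads will be enrolled in a single-arm mixed methods intervention trial" (section 4). The only between-group contrast of changes is the MCI comparison in 16.2.2: "A sub-group analysis will compare the difference in changes from pre to post intervention between dyads". That sentence names no covariates. On group size, section 4.1.1 says: "We will recruit at least 20 dyads of older patients with both advanced cancer and MCI and their caregivers".

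**The concern.** The reference back can only pick up covariates already listed, and the one baseline score among them is the caregiver's distress. For patient scales and patient HRV, that adjusts one person's change for another person's score. For caregiver scales it adjusts for a different construct. In both cases the covariate likely to predict change best, the measure's own TP1 value, is left out, although the plan uses the own baseline for distress.

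Two analysts could fit different models from this sentence. Under the literal model, three things are less precise than they need be: the MCI contrast if it is fitted there, the covariate slopes, and the residual SD that may be carried forward. The last matters because section 16.1 says the quantitative data will guide sample size calculations for a future randomised pilot.

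**Working it through.** **The plan's own figure.** The documents give no precision or power figure for these models. Their one power figure, 83% for 40 dyads in section 16.1, concerns the feasibility rates (0.5 against 0.7, one-sided 0.05). It reproduces: Φ((0.2 − 1.645 × √(0.25/40)) / √(0.21/40)) = 83.3%. It has no bearing on this point.

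**Inputs.** From the documents: 40 dyads, one arm, at least 20 dyads with MCI (20 against 20 used here). Assumed, because the documents give neither: ρ, the correlation between a measure's TP1 and TP2 values, from 0.3 to 0.9; and r, the correlation between the measure's TP1 value and baseline caregiver distress, from 0 to 0.7. Also assumed: equal TP1 and TP2 variances (set to 1), distress related to the TP2 value only through the measure's own TP1 value, and baselines unrelated to MCI status. Gender and income are left out of both models.

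**Formulas.** The change C = TP2 − TP1 has variance 2(1 − ρ).

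- Covariance of C with baseline distress is −r(1 − ρ), so the residual variance after distress is V_D = 2(1 − ρ) − r²(1 − ρ)².
- Covariance of C with the own TP1 value is −(1 − ρ), so the residual variance after own baseline is V_X = 2(1 − ρ) − (1 − ρ)² = 1 − ρ².
- The standard error (SE) of the 20 against 20 contrast is √(V × (1/20 + 1/20)), so the SE ratio is √(V_X / V_D).

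**Worked case, ρ = 0.5 and r = 0.3.** V_D = 1 − 0.09 × 0.25 = 0.9775 and V_X = 0.75. The variance ratio is 0.767, the SE ratio is 0.876, and the SE falls by 12.4%.

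**Range for the MCI contrast.**

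| ρ | V_X | V_D (r = 0 to 0.7) | SE ratio | SE reduction |
|---|---|---|---|---|
| 0.3 | 0.91 | 1.400 to 1.160 | 0.806 to 0.886 | 19.4 to 11.4% |
| 0.5 | 0.75 | 1.000 to 0.878 | 0.866 to 0.925 | 13.4 to 7.5% |
| 0.7 | 0.51 | 0.600 to 0.556 | 0.922 to 0.958 | 7.8 to 4.2% |
| 0.9 | 0.19 | 0.200 to 0.195 | 0.975 to 0.987 | 2.5 to 1.3% |

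A simulation with 40 dyads, r = 0.5 and 10,000 runs gave SE ratios of 0.851, 0.897 and 0.942 at ρ = 0.3, 0.5 and 0.7. The formula gives 0.844, 0.894 and 0.940.

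**Overall mean change.** With covariates centred at their sample means, the fitted intercept is the sample mean of C whichever baseline is used. Its true SD is √(2(1 − ρ)/40), which is √(1/40) = 0.158 at ρ = 0.5. The simulation gave 0.157 under both models, with identical estimates. The model-based SE did fall, from 0.152 to 0.136, but only because regression treats the observed baselines as fixed. That fall is not a gain in precision.

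**Residual SD for planning.** If the future trial adjusts for own baseline and takes its residual variance from the literal model here, its sample size is inflated by V_D / V_X. This is 0.9775/0.75 = 1.30 in the worked case, 0.5775/0.51 = 1.13 at ρ = 0.7 and r = 0.5, and 1.3804/0.91 = 1.52 at ρ = 0.3 and r = 0.2.

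**The case against.** The strongest reply is that the sentence is shorthand: the same structure (pre-measurement, gender, income) applied to each measure with its own pre-value. The oddity of adjusting patient HRV for caregiver distress supports that reading. This stands as a possibility, so the literal reading cannot be treated as settled. It does not remove the need to say which model is meant.

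A reader might infer that the plan throws away precision worth about 30% more dyads across all its exploratory results. The documents do not support that. In a single arm, the mean change has the same true precision under either covariate. Nor does own-baseline adjustment remove regression to the mean from that average, since there is no comparison group. A change score also already uses the TP1 value by subtraction. The variance ratio behind the 30% rests on assumed correlations and applies only to contrasts, slopes and the residual SD.

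Even the MCI gain is conditional. The sub-group sentence does not say the comparison is made in this regression. MCI status is not randomised, so when the groups differ at baseline, the difference in changes and the baseline-adjusted difference answer different questions. The plan names the former. Any association between MCI status and the measure's baseline would also shrink the gain. These objections stand, and they are why both estimates should be shown.

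Finally, aim 1.5.1 concerns the feasibility of collecting HRV, and aim 1.5.2 concerns relationships between measures. Neither is a test of change, which keeps the severity low.

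**Conclusion.** The point holds as a free improvement of low severity. Taken at its word, 16.2.2 adjusts patient and caregiver exploratory changes for caregiver distress and omits each measure's own scheduled baseline. Taken as shorthand, it needs only to be spelled out.

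The benefit to the MCI contrast, if it is fitted in this model with 20 dyads per group, is the SE reduction tabulated above. It is modest at moderate pre-post correlations and negligible at 0.9. It rests on assumed correlations and on baselines unrelated to MCI status. Covariate slopes and the residual SD available for planning the next trial also improve. The precision of the overall mean change, the primary feasibility aim and the caregiver distress model are not affected.

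**What to change.** In section 16.2.2, replace the reference back to the earlier covariates with: using that measure's own TP1 value from the same person, plus gender and income. Fit patient and caregiver measures separately. State whose gender and income are meant, since section 4.1.1 expects 40% + 30% = 70% of dyads to pair a man with a woman. State also whether the outcome is the change or the TP2 value. Once the own TP1 value is in the model, the MCI coefficient is the same either way; without it, it is not.

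If the MCI comparison is made in this model, include the MCI term there and report the unadjusted difference in changes beside it, with a sentence saying that the two answer different questions if baselines differ.

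The cost is a few sentences in the analysis plan and no new data. No observations are lost, even for HRV, because a change cannot be computed without the TP1 value in any case.

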
Interview Script for Patients/Caregivers:

Interviews will cover several broad topics; interviewers will probe participants' responses for more detail as needed.

The same questions will be asked of both patients and caregivers, who will be interviewed separately. Names will be used wherever possible in place of bracketed terms.

1. "What are some strengths you see in this type of intervention?"
 - a. "What did you like most about the intervention?"
2. "What are some limitations you see in the current intervention you were provided information about?"
 - b. "What did you dislike about the intervention?"
3. "How do you feel about the length of the total intervention?"
4. "How do you feel about the length of each session?"
5. "How suitable is this intervention give your current demands and daily responsibilities?"
6. "What, if any, are memories or experiences you feel you would not want to share with [caregiver/patient]?"
7. "What, if any, are some memories or experiences you feel are most important to share with your caregiver?"
8. "What were your impression of the first half of the intervention (weeks 1-4), how did you feel about sharing about your childhood, adolescents, and young adulthood?"
9. "What were your impression of the second half of the intervention (weeks 4-8), how did you feel about sharing about middle age and more recent memories and experiences?"
10. "What would you have changed about this dyadic life review intervention?"
11. How did this intervention help your relationship with your partner?
12. "How do you cope with this illness?"
 - a. "Have [repeat identified coping strategies] changed since doing this dyadic life review?"
 - b. "If so, how have they changed?"
13. "What does coping look like between you and your partner?"
 - a. "Can you give examples of what that looks like?"
14. "If you experienced loneliness or a sense of isolation before this, how did that change during the intervention?"
 - a. "If these experiences did change for you, what helped this to change?"
15. "If you're willing, what were some things you and [caregiver/patient] talked about on the way home from the session or the night after that session?"
16. "Is there any other feedback about the intervention you would like to provide?"

Dyadic Life Review Intervention Guide:

Session 1: Childhood

Welcome and thank you for your time today. Today we will be focusing on each of your childhood experiences. I will have some questions to help us get started with our conversation. There is no right or wrong response. You are free to move through memories as they come and I [the interventionist] may prompt for more detail or information as you recall these events.

[Direct questions to first patient then the caregiver, when possible use patient and caregivers' names to support building rapport through this process]

1. How are you feeling today?
2. Let's take a minute and have your minds take you back to your childhood, birth through 13. Tell me a memory that first comes to your mind?
 - 2a. [Caregiver] What did this memory [Patient] just share make you feel or think about?
What was the first memory that came to mind for you [caregiver]?
 - 2b. [Patient] What did this memory [Caregiver] just share make you feel or think about?
3. Who was most influential in your life during this period?
 - 3a. [Caregiver] What did this memory [Patient] just share make you feel or think about?
Who was most influential for you in your childhood [caregiver]?
 - 3b. [Patient] What did this memory [Caregiver] just share make you feel or think about?
4. Tell me about your favorite place during childhood?
 - 4a. [Caregiver] What did this memory [Patient] just share make you feel or think about?
Tell me, [Caregiver] about your favorite place during childhood?
 - 4b. [Patient] What did this memory [Caregiver] just share make you feel or think about?

Session 2: Adolescence

Welcome and thank you for your time today. Today we will be focusing on each of your adolescent experiences. I will have some questions to help us get started with our conversation. There is no right or wrong response. You are free to move through memories as they come and I [the interventionist] may prompt for more detail or information as you recall these events.

[Direct questions to first patient then the caregiver, when possible use patient and caregivers' names to support building rapport through this process]

1. How are you feeling today?
2. Let's take a minute and have your minds take you back to your adolescence. Tell me a memory that first comes to your mind from this period of your life?
 - 2a. [Caregiver] What did this memory [Patient] just share make you feel or think about?
What was the first memory that came to mind for you [caregiver]?
 - 2b. [Patient] What did this memory [Caregiver] just share make you feel or think about?
3. Who was most influential in your life during this period?
 - 3a. [Caregiver] What did this memory [Patient] just share make you feel or think about?
Who was most influential for you in your adolescence[caregiver]?
 - 3b. [Patient] What did this memory [Caregiver] just share make you feel or think about?
4. What were your most pleasant memories about your adolescence?
 - 4a. [Caregiver] What did this memory [Patient] just share make you feel or think about?
Tell me, [Caregiver] what were your most pleasant memories from your adolescence?
 - 4b. [Patient] What did this memory [Caregiver] just share make you feel or think about?

Session 3: Young Adulthood (20-35 years)

Welcome and thank you for your time today. Today we will be focusing on each of your young adulthood experiences. I will have some questions to help us get started with our conversation. There is no right or wrong response. You are free to move through memories as they come and I [the interventionist] may prompt for more detail or information as you recall these events.

[Direct questions to first patient then the caregiver, when possible use patient and caregivers' names to support building rapport through this process]

1. How are you feeling today?
2. Let's take a minute and have your minds take you back to your young adulthood, 19-35. Tell me a memory that first comes to your mind?

2a. [Caregiver] What did this memory [Patient] just share make you feel or think about?

What was the first memory that came to mind for you [caregiver]?

2b. [Patient] What did this memory [Caregiver] just share make you feel or think about?

3. What was life like for you in your 20's and early 20's?

3a. [Caregiver] What did this memory [Patient] just share make you feel or think about?

What was life like for you during this period [caregiver]?

3b. [Patient] What did this memory [Caregiver] just share make you feel or think about?

4. Tell me about your work? If you did not work, tell me about the activities or roles you spent the most time in?

4a. [Caregiver] What did this memory [Patient] just share make you feel or think about?

Tell me, [Caregiver] about your work, or if you did not work, your primary activities or roles during this time in your life?

4b. [Patient] What did this memory [Caregiver] just share make you feel or think about?

5. If applicable to patient/caregiver:

For romantically involved dyads: Did you two meet during this time period? If so, tell me about this time and what you felt? What you thought about?

5a. [Caregiver] What did this memory [Patient] just share make you feel or think about?

For parent/adult child dyads: What was it like becoming a parent during this time?

5b. [Caregiver] What did this memory [Patient] just shared about becoming a parent make you feel or think about?

*Note: these questions from 5 can be shifted to whichever time period session the patient met their significant other caregiver, friend caregiver, or to the period they became a parent if it does not fall within this period.

Session 4: Dyadic Processing and Review of Session 1-3

Welcome and thank you for your time today. Today we will be focusing on reviewing what you have each shared up to this point. I will have some questions to help us get started with our conversation. There is no right or wrong response. You are free to move through memories as they come and I [the interventionist] may prompt for more detail or information as you recall these events.

[Direct questions to first patient then the caregiver, when possible use patient and caregivers' names to support building rapport through this process]

1. How are you feeling today?
2. Let's take a minute and recall some of the memories both [Patient] and [Caregiver] shared over the first three sessions.
 - 2a. [Patient] what has stood out to you up to this point about what [Caregiver] has shared thus far?
[Caregiver] what about you? What has stood out?
 - 2b. [Patient] Is there a memory you haven't shared so far that you are particularly proud to share with [Caregiver]?
[Caregiver] what about you? Is there a particular memory you have shared or still would like to share that you are particularly proud of?
3. [Patient] how would you describe your perception of [Caregiver] after recalling periods of your life together?
 - 3a. [Caregiver] how would you describe your perception of [Patient] after recalling these periods of life together?
4. We have talked about a large portion of your lives so far, share with me your overall feelings about these memories and periods of your life.
 - 4a. [Caregiver] What did what [Patient] just share make you feel or think about?
Tell me, [Caregiver] about your overall feelings about these memories or period of your life.
 - 4b. [Patient] What did what [Caregiver] just share make you feel or think about?

Session 5: Mid-Life (35-50 years)

Welcome and thank you for your time today. Today we will be focusing on each of your mid-life experiences. I will have some questions to help us get started with our conversation. There is no right or wrong response. You are free to move through memories as they come and I [the interventionist] may prompt for more detail or information as you recall these events.

[Direct questions to first patient then the caregiver, when possible use patient and caregivers' names to support building rapport through this process]

1. How are you feeling today?
2. Let's take a minute and have your minds take you back to your mid-life, 35-50 years of age. Tell me a memory that first comes to your mind?
 - 2a. [Caregiver] What did this memory [Patient] just share make you feel or think about?
What was the first memory that came to mind for you [caregiver]?
 - 2b. [Patient] What did this memory [Caregiver] just share make you feel or think about?
3. Who was most influential in your life during this period?
 - 3a. [Caregiver] What did this memory [Patient] just share make you feel or think about?
Who was most influential for you in your mid-life [caregiver]?
 - 3b. [Patient] What did this memory [Caregiver] just share make you feel or think about?
4. How do you feel you have changed from the earlier periods of life to this time period?
 - 4a. [Caregiver] What did what [Patient] just share make you feel or think about?
[Caregiver] How do you feel you have changed from the earlier periods of life to this time period?
 - 4b. [Patient] What did what [Caregiver] just share make you feel or think about?

Session 6: Early late life (50-65 years)

Welcome and thank you for your time today. Today we will be focusing on each of your early late life experiences. I will have some questions to help us get started with our conversation. There is no right or wrong response. You are free to move through memories as they come and I [the interventionist] may prompt for more detail or information as you recall these events.

[Direct questions to first patient then the caregiver, when possible use patient and caregivers' names to support building rapport through this process]

1. How are you feeling today?
2. Now we are going to reflect on early late life, ages 50-65 years. Tell me a memory that first comes to your mind?
 - 2a. [Caregiver] What did this memory [Patient] just share make you feel or think about?
What was the first memory that came to mind for you [caregiver]?
 - 2b. [Patient] What did this memory [Caregiver] just share make you feel or think about?
3. Who was most influential in your life during this period?
 - 3a. [Caregiver] What did this memory [Patient] just share make you feel or think about?
Who was most influential for you in your childhood [caregiver]?
 - 3b. [Patient] What did this memory [Caregiver] just share make you feel or think about?
4. Tell me about your friendships or relationships during this period?
 - 4a. [Caregiver] How did this what [Patient] just share make you feel or think about?
Tell me, [Caregiver] about your friendships or relationships during this period?
 - 4b. [Patient] How did what [Caregiver] just share make you feel or think about?

****For some caregiver enrolled, this may be the present age period for them. If so the questions are still relevant, but also consider adding:***

5. [Caregiver] are there any other really important memories that come to mind from the periods we discussed so far?
 - 5a. [Caregiver] Why do you think these came to mind for you today?
 - 5b. [Patient] How did what [Caregiver] just share make you feel?
 - 5c. [Caregiver] What pieces of wisdom would you like to hand down to younger generations?

Session 7: Later Life (65+ years)

Welcome and thank you for your time today. Today we will be focusing on each of your late life experiences. I will have some questions to help us get started with our conversation. There is no right or wrong response. You are free to move through memories as they come and I [the interventionist] may prompt for more detail or information as you recall these events.

[Direct questions to first patient then the caregiver, when possible use patient and caregivers' names to support building rapport through this process]

1. How are you feeling today?
2. Today we will discuss the present time period of life. What was the most influential event from this period?
 - 2a. [Caregiver] What did this memory [Patient] just share make you feel or think about?
What was the first memory that came to mind for you [caregiver]?
 - 2b. [Patient] What did this memory [Caregiver] just share make you feel or think about?
3. Tell me about your friendships and relationships during this period of life?
 - 3a. [Caregiver] What did what [Patient] just share make you feel or think about?
[Caregiver] Tell me about your friendships and relationship during this period of life?
 - 3b. [Patient] What did this memory [Caregiver] just share make you feel or think about?
4. In your entire life, what relationship stands out as most influential?
 - 4a. [Caregiver] What did this memory [Patient] just share make you feel or think about?
 - 4b. [Caregiver], in your entire life, what relationship stands out as most influential?
[Patient] What did this that [Caregiver] just shared make you feel?
5. [Patient] What pieces of wisdom would you like to hand down to younger generations?
Note: If caregiver's age falls within this period:
 - 5a. [Caregiver] What pieces of wisdom would you like to hand down to younger generations?

Session 8: Final Session Dyadic Processing and Review

Welcome and thank you for your time today. Today we will be focusing on a review of our 8 weeks together and the memories you have each shared. I will have some questions to help us get started with our conversation. There is no right or wrong response. You are free to move through memories as they come and I [the interventionist] may prompt for more detail or information as you recall these events.

[Direct questions to first patient then the caregiver, when possible use patient and caregivers' names to support building rapport through this process]

1. How are you feeling today?
2. [Patient] What was the most meaningful memory to you that [Caregiver] shared during this time together?
 - 2a. [Caregiver] What did what [Patient] just share make you feel or think about?
[Caregiver] What was the most meaningful memory to you that [Patient] shared during this time together?
 - 2b. [Patient] What did what [Caregiver] just share make you feel or think about?
3. Do you feel you have lived your life as you hoped to live it?
 - 3a. [Caregiver] What did what [Patient] just share make you feel or think about?
[Caregiver] do you feel you have lived your life as you hoped to live it?
 - 3b. [Patient] What did what [Caregiver] just share make you feel or think about?
4. [Patient] What is one thing you want to tell [Caregiver] after hearing about these periods of their life?
 - 4a. [Caregiver] What did what [Patient] just share make you feel or think about?
[Caregiver] What is one thing you want to tell [Patient] after hearing about these periods of their life?
 - 4b. [Patient] What did what [Caregiver] just share make you feel or think about?
